**Table 6: SAEs that do not require reporting**

| Expected SAE   | Process                        |
|--|--------------------------------|
| Pre-planned hospitalisation  |                                |
| SAEs related to pre-existing condition                                       |                                |
| SAEs that are related to symptoms or progression of the participants disease | Document in medical notes only |

All events which meet the definition of serious must be recorded in the participant notes, including the causality and severity, throughout the participant's time on trial, including follow-up, but for trial purposes these events do not require reporting on the SAE Form. Such events are "safety reporting exempt".

## 10.5.2 Serious Adverse Events requiring non-expedited reporting to the Trial Office

Where the safety profile is well established, the causal relationship between the intervention (or the participant's underlying condition), and the SAE, may be known. That is, such events are protocol-defined as "expected" (see Section 10.6.2 Assessment of expectedness of an SAE by the CI).

Such events should still be recorded by the trial team in the participant's medical notes and on the relevant Case Report Forms (CRFs), but do not require expedited reporting (immediately on the site becoming aware of the event) since the assessment of expectedness for the specified events has been pre-defined.

### 10.5.2.1 All Participants

AEs are commonly encountered in patients undergoing an emergency laparotomy or laparoscopy. As part of the TONIC trial, we will also be collecting surgical complications (as detailed below), these will be collected for the trial related emergency laparotomy or laparoscopy (the index surgery), and will be recorded on trial specific CRFs:

**Table 7: TONIC Trial SAEs requiring non-expedited reporting for all participants**

| Expected SAE                                   | Process                                    |
|--|--|
| Urinary tract infection                        |  |
| Acute kidney injury (not present at admission) |  |
| Pneumonia                                      |  |
| Atrial fibrillation                            |  |
| Myocardial infarction                          |  |
| Cerebrovascular accident                       | Report on the relevant trial specific CRFs |
| Deep vein thrombosis                           |  |
| Pulmonary embolism                             |  |
| Delirium                                       |  |
| Intra-abdominal collection                     |  |
| Superficial surgical site infection            |  |
| Deep surgical site infection                   |  |

|                                     |  |
|-------------------------------------|--|
| Superficial (skin) dehiscence       |  |
| Fascial (abdominal wall) dehiscence |  |
| Anastomotic leak                    |  |
| Unplanned ICU admission             |  |

#### 10.5.2.2 Participants randomised to PN

All participant randomised to PN should start PN within 48 hours of their operation. The safety of PN is well established and it's highly unlikely that the trial will reveal any new safety information relating to this intervention. Therefore, a strategy of targeted reporting of AEs will not affect the safety of participants. We will only collect specific AEs and side effects that have a high probability of being related to PN (as detailed below) and these will be recorded on trial specific CRFs.

**Table 8: TONIC Trial SAEs requiring non-expedited reporting for participants allocated to PN**

| Expected SAE   | Process   |
|--|---|
| Hospital admissions lasting less than 24 hours   | To be reported on trial-specific follow-up CRF    |
| Surgical complications   | To be reported on the relevant trial specific CRF |
| Hypoglycaemia  |   |
| Hyperglycaemia   |   |
| Hypokalaemia   |   |
| Refeeding syndrome   |   |
| Cholestasis  |   |
| PICC/CVC complications:  | Report on the relevant trial specific CRFs        |
| 
 
• Pneumothorax
 
• Line infection
 
• Line fracture
 
• Line occlusion
 
• Line thrombosis
 
 |   |

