### 7.2 Trial intervention: Parenteral Nutrition

The trial intervention is intentionally pragmatic. Patients randomised to the intervention arm will receive early PN which will be administered intravenously and should be delivered either through a dedicated lumen of a central line placed at operation, or through a PICC line. These lines are inserted by anaesthetists or by specialised vascular access services, depending on local service specifications. Line access may be secured at any point from randomisation to commencement of intervention. Placement of these lines will be confirmed with a plain radiograph of the chest and is undertaken as per local processes, using aseptic techniques. Blood tests are performed prior to commencement of PN to ensure sodium, potassium, magnesium, and phosphate are in the correct range

PN is available pre-formulated from multiple suppliers in the UK. The trial does not specify or mandate the use of any particular brand; participating sites should continue to use the PN formulation routinely employed in their standard clinical practice. Sites will already have familiarity with a particular brand and will use this for the trial. PN provides carbohydrates, lipids, amino acids, vitamins, trace elements, electrolytes and water. These amounts vary according to the supplied bag. An appropriate base PN bag is selected based upon the nutrients required, particularly calories. Additional electrolytes can be added, tailored to the patient's biochemistry. The administration of PN is defined in UK guidance from NICE[26], which provides guidance on calculating calorie requirements. Sites will calculate appropriate rates of PN to be administered prior to commencement. Out of hours, this may include administering a volume defined by local out-of-hours feeding protocols, rather than a dose tailored to exact calorie requirements. At the commencement of PN, dosing is at a reduced rate to avoid metabolic consequences. This is slowly increased with ongoing monitoring of blood tests for evidence of electrolyte disturbance (e.g. abnormal sodium, potassium, phosphate, or magnesium levels). Blood tests (biochemistry including renal and liver function) are required daily for the first week of administration and

---

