| Assessment of patient treatment satisfaction Visual Analog Scale (VAS)            |           |          |                    |   |              | ✓                  | ✓                  |
| Health Resource Use Questionnaire Form  |           | ✓        |                    |   |              | ✓                  | ✓                  |
| Safety and complications   |           |          |                    |   |              |                    |                    |
| Side effects/adverse events   |           |          | ✓                  | ✓   | ✓            | ✓                  | ✓                  |
| Nutrition intervention related complications including metabolic and line-related |           |          | ✓                  | ✓   | ✓            | ✓                  | ✓                  |
| Process measures   |           |          |                    |   |              |                    |                    |
| Use and duration of PN/ other nutritional interventions                           |           |          |                    |   | ✓            | ✓                  | ✓                  |
| Time to line insertion & time to commence PN                                      |           |          |                    | ✓   |              |                    |                    |

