## **10.3 Adverse event reporting period**

The reporting period for AEs and Serious Adverse Events (SAEs) in TONIC will be:

- For PN related SAEs: from the day of PN until the end of the trial (90 days post-operation).
- For surgery related SAEs: from the day of surgery until the end of the trial (90 days post-operation).

The overall defined reporting period will end 90 days post-operation. After the participant has reached 90 days post-operation, sites will not be actively following up participants for SAEs.

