#### **14.2.2 Secondary outcomes**

Secondary outcomes will be analysed for the intention to treat analysis population. Binary outcomes will be analysed using logistic regression with covariates of minimisation factors. The treatment difference will be reported as an OR with corresponding 95% confidence interval. Continuous secondary outcomes such as questionnaires and patient-reported outcome measures (PROMs) will be analysed analogously to the primary outcome using linear regression (95% confidence intervals will not be bootstrapped). Length of hospital stay will be log-transformed analysed using linear regression: summaries on mean fold difference and absolute difference will be presented.

For safety outcomes and adverse events, the following summaries will be presented: the number and percentages of patients reporting SAEs in each arm. In addition, the number of participants requiring further interventions or revisions will be summarised descriptively.

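### The protocol names metabolic and most line-related SAEs for reporting only in participants allocated to PN, yet summarises SAEs by arm; its other reporting rules conflict on how a control-arm event is handled

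*Protocol*

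**What the plan says.** **Two lists.** Table 7 in Protocol section 10.5.2.1 is headed "TONIC Trial SAEs requiring non-expedited reporting for all participants". Its 16 surgical and medical events include no glucose, electrolyte, refeeding, cholestasis or line event. Section 10.5.2.2 is headed for participants randomised to PN and states: "We will only collect specific AEs and side effects that have a high probability of being related to PN". Its Table 8, "TONIC Trial SAEs requiring non-expedited reporting for participants allocated to PN", holds the metabolic and liver events and five PICC/CVC complications: pneumothorax, infection, fracture, occlusion and thrombosis. The trigger is allocation, not exposure to PN or to a line.

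**Control-arm exposure.** Sections 7.1 and 7.3 allow PN in the control arm from day 5, or earlier where the clinical need is pressing.

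**Analysis.** For safety, section 14.2.2 presents "the number and percentages of patients reporting SAEs in each arm".

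**Rules without an arm limit.** Table 4 in section 9.1 schedules "Nutrition intervention related complications including metabolic and line-related" from surgery to day 90. Item 3 of section 10.5 sends every SAE outside the exempt and non-expedited categories to expedited reporting under 10.5.3. Section 10.5.3 itself requires that only for death, serious line infection, and other SAEs that are both related and unexpected.

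**Time window.** Section 10.3 sets the period as "For PN related SAEs: from the day of PN until the end of the trial", with a separate period for surgery-related SAEs from the day of surgery. Section 7.2 says "Line access may be secured at any point from randomisation to commencement of intervention", and section 6.3 places randomisation before the operation.

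**The concern.** A by-arm SAE percentage can be read as a treatment effect only if the same events are sought in the same way in both arms. Here the non-expedited list is longer for the PN arm. The extra events are the ones that section 3.4 gives as the main risks of PN: electrolytes, glucose, liver function and line infection. Some of them also occur without early PN, after late PN in a control participant or from emergency surgical illness itself. If sites follow the table titles, the PN arm accumulates events that go unrecorded in control. The direction is predictable, towards apparent harm from PN. The safety data supplied to the DMC under section 16.6 would carry the same imbalance. Control events that were not prompted for at the time cannot be fully recovered at analysis.

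The late-opening window works the other way. A harm from line insertion before PN starts, or in someone who has a line but never starts PN, can drop out of the PN-related count.

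**Working it through.** **1. The plan's own figure.** The only stated figure used here is the sample size, and it is not in dispute. With a difference of 6, SD 27, 5% two-sided and 90% power: n = 2 × (1.96 + 1.2816)² × 27² / 6² = 426 per arm; 426 / 0.95 = 449 per arm, 898 in total. This agrees with section 14.1. The illustration below uses 449 per arm.

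**2. One event followed through the rules.** Take a serious hyperglycaemia or a line thrombosis.
- PN arm: Table 8 applies, so it is recorded on a trial CRF without expedition.
- Control arm, Table 7: not listed.
- Control arm, Table 4: scheduled for collection, with no SAE route given.
- Control arm, section 10.5 item 3: outside the first two categories, so an expedited report within 24 hours.
- Control arm, section 10.5.3: neither death nor line infection, so expedited only if related and unexpected. Section 10.6.1 judges relatedness against early PN or the operation, so an event due to late PN does not obviously qualify. Section 10.6.2 treats an event as unexpected if the protocol does not define it as expected, and Table 8 lists these events under that label.

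The same event is thus a routine entry in one arm and, in the other, either a 24-hour report or not reportable. Sites cannot follow both control-arm rules.

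**3. Size of the false difference.** The Protocol gives no rates for Table 8 events, so all of these are assumptions:
- b, share with an SAE from some other source: 20%, 30% or 47% (the top value is the upper morbidity figure in section 1.1).
- r, share of the rest with a serious Table 8 event only: 2%, 5% or 10%, equal in both arms.
- c, share of those events captured in control: 0 or 0.5.

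PN arm = b + (1 − b)r. Control = b + (1 − b)rc. False excess = (1 − b)r(1 − c).

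With c = 0:

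| b | r | PN | Control | Excess (points) | OR | Chance of p < 0.05 if tested |
|---|---|---|---|---|---|---|
| 20% | 2% | 21.6% | 20.0% | 1.6 | 1.10 | 9% |
| 20% | 5% | 24.0% | 20.0% | 4.0 | 1.26 | 30% |
| 20% | 10% | 28.0% | 20.0% | 8.0 | 1.56 | 80% |
| 30% | 2% | 31.4% | 30.0% | 1.4 | 1.07 | 7% |
| 30% | 5% | 33.5% | 30.0% | 3.5 | 1.18 | 20% |
| 30% | 10% | 37.0% | 30.0% | 7.0 | 1.37 | 60% |
| 47% | 2% | 48.1% | 47.0% | 1.1 | 1.04 | 5% |
| 47% | 5% | 49.7% | 47.0% | 2.7 | 1.11 | 12% |
| 47% | 10% | 52.3% | 47.0% | 5.3 | 1.24 | 36% |

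The last column is Φ[(excess − 1.96 × SE₀)/SE₁] with 449 per arm. For b = 30% and r = 10%, SE₀ = √(2 × 0.335 × 0.665 / 449) = 0.0315 and SE₁ = √[(0.37 × 0.63 + 0.30 × 0.70) / 449] = 0.0314, so Φ[(0.07 − 1.96 × 0.0315)/0.0314] = Φ(0.26) = 0.60.

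With c = 0.5 every excess halves, giving about 0.5 to 4.0 points. With c = 1 (same list in both arms) it is zero.

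**4. The window.**
- Line placed after randomisation but before the day of surgery: outside both periods in section 10.3, and before the first Table 4 tick for line-related complications.
- Line harm from the day of surgery but before the day of PN: inside the surgery-related period, so counted only if classed as surgery-related. Table 4 does schedule its collection.
- From the day of PN: covered.

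**The case against.** The strongest reply is that Table 8 sets a reporting route and does not forbid collection in control. Table 4 has no arm limit. Vascular line infection is an in-hospital secondary outcome in both arms (section 8.2.2.1). Serious line infection is expedited in either arm (Table 9). Section 10.5 item 3 is a catch-all. This stands to the extent that one cannot say control-arm events are never collected. It does not cure the problem, because these passages conflict with Table 8 and the catch-all conflicts with section 10.5.3.

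Two Table 8 rows give little ground for concern. Surgical complications are collected for everyone under section 10.5.2.1 and Table 7. Admissions under 24 hours overlap with unplanned readmissions, which are recorded in both arms at days 30 and 90.

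Section 14.2.2 also describes a summary of counts and percentages, not a test. A p-value for SAEs would follow only from a broad reading of the sentence in section 14.2 that covers all outcomes.

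A reader might infer that the primary outcome is biased too. The text does not support that. Section 9 takes in-hospital complications from the notes and the treating team, section 14.2.1 uses all recorded complications, neither differs by arm, and nothing makes the Table 8 forms a source for the CCI. With unblinded assessors (section 6.6), prompts in one arm only would be a risk if the forms were built that way, but that is not shown.

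A reader might also apply the frequency of any glucose or electrolyte disturbance and expect a far larger gap. Table 8 is an SAE list, and section 10.4 says that non-serious events are not reported to the trial team. The looser mention of AEs and side effects in section 10.5.2.2 blurs this but is not enough to justify any-event rates.

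**Conclusion.** The point holds for the safety summary. Section 10.5.2 makes the SAE list depend on allocation, the control arm can have the same events, and section 14.2.2 reports SAEs by arm. The passages that might restore symmetry contradict one another. If Table 8 is applied as titled and control events go uncaptured, the PN arm shows a false excess of about 1 to 8 percentage points (OR 1.04 to 1.56), or about 0.5 to 4 points if half are captured. These sizes rest wholly on assumed rates, equal in both arms; the direction, an inflated PN-arm percentage, does not depend on the particular values chosen. The window gap is real but narrow: complete only for a line placed before the day of surgery, and conditional on how the event is classed between surgery and PN. The sample size is unaffected, and no effect on the CCI is shown. This should be fixed, as a defect of the safety reporting only.

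**What to change.** 1. Move the metabolic, refeeding, cholestasis and PICC/CVC rows of Table 8 into an all-participants list. Collect them on the same CRF at the same times in both arms, as Table 4 already implies.
2. Reconcile section 10.5 item 3, section 10.5.3 and Table 4, so that each of these events has one reporting route that does not depend on allocation.
3. In section 10.3, open the reporting period for line-related events at randomisation or first line insertion, and align the Table 4 row with it.

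The cost is protocol wording, one CRF common to both arms and slightly more data entry for control participants. The sample size stays at 898 and the planned analyses do not change.

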### **10.5.3 Serious Adverse Events requiring expedited reporting to the Trial Office**

The SAEs listed in Table 9 require expedited reporting. These should be reported as outlined in table 9.

**Table 9: SAE that require expedited reporting**

| Expected SAE   | Process  |
|--|--|
| Death  |  |
| Line infection – if it leads to systemic sepsis, requires escalation to HDU/ITU, or is considered medically significant by the investigator. | Report on SAE Form and provide to the TONIC Trial Office within 24 hours of becoming aware of the event. |

Any other SAEs that are related and unexpected would require expedited reporting to the trial office.

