## 10. ADVERSE EVENT REPORTING

### 10.1 Definitions

Table 5: Definitions for Adverse Events

|   |          |   |
|---|----------|---|
| Severity Definitions                         | Mild     | Awareness of signs or symptoms that do not interfere with the participant's usual activity or are transient and resolved without treatment and with no sequelae.  |
|   | Moderate | A sign or symptom, which interferes with the participant's usual activity.  |
|   | Severe   | Incapacity with inability to do work or perform usual activities (including life threatening events and fatality).  |
| Adverse Event                                | AE       | Any untoward medical occurrence in a participant participating in the trial which does not necessarily have a causal relationship with the intervention received.   |
| Related Event                                | RE       | An event which resulted from the administration of any of the research procedures.  |
| Serious Adverse Event                        | SAE      | An untoward occurrence that:
Results in death
Is life-threatening*
Requires hospitalisation or prolongation of existing hospitalisation
Results in persistent or significant disability or incapacity
Consists of a congenital anomaly/ birth defect
Or is otherwise considered medically significant by the Investigator** |
| Unexpected Event                             | UE       | The type of event that is not listed in the protocol as an expected occurrence.   |
| Related and Unexpected Serious Adverse Event | N/A      | A SAE that meets both the definition of a Related and Unexpected Event.   |

\* The term life-threatening is defined as diseases or conditions where the likelihood of death is high unless the course of the disease is interrupted.

\*\* Medical events that may not be immediately life-threatening or result in death or hospitalisation but may jeopardise the participant or may require intervention to prevent one of the other outcomes listed in the definitions above.

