## **10.5 Serious Adverse Events reporting in TONIC**

It is recognised that the frequency of SAEs in this participant population may be high. Many of these SAEs will be anticipated due to the potential of either the operation or PN undertaken by the participant. We have therefore outlined anticipated SAEs that do not require reporting and anticipated SAEs that do not require expedited reporting.

---

For all SAEs, the PI or delegate must do one of the following:

1. **Record safety reporting-exempt SAEs** in the medical notes but **not report** them to the trials office as per Section 10.5.1.
2. **Report SAEs to the trial office in a non-expedited manner.** This can only be done for the pre-defined subset of SAEs as per Section 10.5.2.
3. **Report SAEs to the trial office in an expedited manner** (within 24 hours of the site research team becoming aware of the event). All SAEs not covered by the above 2 categories must be reported as per Section 10.5.3.

**Note:** when an SAE occurs at the same hospital at which the participant is receiving trial intervention or is being followed up for trial purposes, processes must be in place to make the trial team at the hospital aware of any SAEs, regardless of which department first becomes aware of the event, in an expedited manner.

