### **10.6.1 Assessment of causality of an SAE**

When completing the SAE form, the PI (or, throughout this section, a medically qualified delegate) will be asked to define the nature of the seriousness and causality (relatedness; see Table 10: Categories of causality) of the event.

In defining the causality the PI must consider if any concomitant events or medications may have contributed to the event and, where this is so, these events or medications should be reported on the SAE form. It is not necessary to report concomitant events or medications which did not contribute to the event.

As per Table 10, all events considered to be 'possibly', 'probably', or 'definitely' related to the intervention (i.e. early PN) or operation, will be reported by the trial office as 'related'; all events considered at site to be 'unlikely' or 'unrelated' to the intervention will be reported by the trials office as 'unrelated'. The same categorisation should be used when describing AEs and protocol-exempt SAEs in the source data.

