### 10.6.2 Assessment of expectedness of an SAE by the CI

The CI or delegate(s) will also assess all related SAEs for expectedness with reference to the criteria in Table 11: Categories of expectedness.

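### Sections 10.5 and 10.5.3 conflict on whether an unlisted SAE judged unrelated is reported, and Table 8 sends the same event down different routes by arm

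*Protocol*

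**What the plan says.** Protocol Section 10.5 gives one rule for all SAEs: the investigator takes one of three routes. Exempt events (Table 6) are only noted in the medical record. Events on the non-expedited lists (Tables 7 and 8) go on trial CRFs. Everything else is expedited, "within 24 hours of the site research team becoming aware of the event", and the catch-all reads: "All SAEs not covered by the above 2 categories must be reported as per Section 10.5.3". Relatedness plays no part in that sorting.

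Section 10.5.3 puts death and the more severe line infections in Table 9 and then adds: "Any other SAEs that are related and unexpected would require expedited reporting to the trial office".

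Other text bears on the point:

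- Section 10.1, Table 5, defines an unexpected event: "The type of event that is not listed in the protocol as an expected occurrence".
- Section 10.6.1 treats an event as related if it is at least possibly "related to the intervention (i.e. early PN) or operation". It also says how the Trial Office classes events that sites rate as unlikely or unrelated. The Chief Investigator then reviews causality independently, and a judgement of related from either party is enough.
- Section 10.6.2 states: "The CI or delegate(s) will also assess all related SAEs for expectedness". It adds that the Chief Investigator reviews every SAE.
- Table 7 lists 16 events for all participants. Table 8 lists metabolic, line and other events only for participants allocated to PN, although Sections 7.1 and 7.3 allow PN in the control arm.
- Section 14.2.2 will present "the number and percentages of patients reporting SAEs in each arm".

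**The concern.** Sites need one instruction for a serious event that appears on none of the lists. Here the general rule sends them to a section that states a narrower one. Under the narrower rule, the site's view of causality decides whether the event is sent at all. That view is the one the central review in Section 10.6 is meant to check, and an event that is never sent cannot be reclassified.

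Two things are at stake: central safety oversight, and the completeness of the SAE percentages to be reported by arm. The second is also exposed to Table 8, because a list that applies to one arm only means that identical events are collected by different routes.

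**Working it through.** No arithmetic applies, since the protocol states no SAE rates. The check follows each kind of SAE through the two sections.

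| SAE | Section 10.5 | Section 10.5.3 |
|---|---|---|
| (a) In none of Tables 6 to 9, judged related | 24-hour report | 24-hour report: unlisted means unexpected under Table 5 |
| (b) In none of Tables 6 to 9, judged unlikely or not related | 24-hour report | No route |
| (c) Table 8 event (e.g. cholestasis, line thrombosis), PN arm | Trial CRF, non-expedited | Not applicable |
| (d) Same event as (c), control arm | Not in Table 7, so 24-hour report | Not clearly reportable |
| (e) Surgical complication outside Table 7, PN arm | Covered by the general surgical-complications row of Table 8, so trial CRF | Not applicable |
| (f) Same event as (e), control arm | Not in Table 7, so 24-hour report | Depends on whether the Table 8 row makes it expected |

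**Row (b)** is the conflict. The rest of Section 10 presupposes the broad rule. Section 10.6.1 has categories for unlikely and not related and says how the Trial Office classes such events, and the Chief Investigator reviews causality independently and looks at all SAEs. None of this can happen for an event that was filtered out at site.

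**Row (d)** is unclear under Section 10.5.3 for two reasons. The causality test refers to early PN or the operation, and PN started later in a control participant is not early PN. In addition, the protocol names the event as expected, although only in a table for the other arm.

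**Rows (c) to (f)** show a difference by arm even if Section 10.5 is followed to the letter: a CRF entry in one arm, a 24-hour SAE form in the other.

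**Effect on the summary by arm.** Suppose a proportion p1 of the PN arm and p0 of the control arm have row (b) events as their only SAEs. If these go unreported and are captured nowhere else, the reported percentages fall by p1 and p0, and the difference between arms shifts by p0 − p1. The protocol gives neither proportion. If they are equal, both percentages are too low but the difference is unchanged.

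**The case against.** The strongest reply is that Section 10.5 is mandatory and exhaustive, while Section 10.5.3 nowhere says that unrelated SAEs are not to be sent, so the gap is inferred from silence. Sections 10.6.1 and 10.6.2 also fit the broad rule. This shows which rule was probably meant. It does not remove the problem, because Section 10.5 refers sites to 10.5.3, and what they find there is a condition on relatedness.

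The mitigation stands. Deaths are expedited whatever the cause. Table 6 removes some unrelated events under either reading. Complications are collected in both arms at discharge, day 30 and day 90, and Table 4 schedules adverse events and nutrition-related complications without restricting them by arm. None of this replaces 24-hour notification or central causality review.

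Three stronger readings are tempting, and the documents do not support them:

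- *Related but expected SAEs also fall into the gap.* Under Table 5 an unlisted event is unexpected by definition, so an unlisted related SAE is expedited under both sections. Table 11 words expectedness more loosely, but the sentence after it returns to the protocol's own list. This limb is close to empty.
- *Section 10.5.3 inflates SAEs in the PN arm.* Related also covers the operation, which applies in both arms, and controls may receive PN. Differing attribution in an unblinded trial is plausible, but the protocol gives nothing from which to establish its direction or size.
- *The Data Monitoring Committee is misled.* Section 16.6 provides it with safety outcomes and, where appropriate, primary and major secondary outcomes. Distortion of its view is not shown.

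**Conclusion.** The contradiction is real but narrow. It concerns SAEs in none of Tables 6 to 9 that the site judges unlikely or not related: Section 10.5 requires a report within 24 hours, and Section 10.5.3 does not. If sites follow 10.5.3, these events miss the Chief Investigator's review and, unless captured elsewhere, the SAE summary by arm. A separate asymmetry lies in Table 8, which routes the same event differently by arm.

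The effect is on SAE oversight and on the SAE percentages by arm, not on the primary outcome. Its size is unknown, because it depends on how often such events occur and on which section sites follow, and the protocol gives neither. The correction should be made because it is cheap and concerns safety reporting.

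**What to change.** Make two changes in one amendment.

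1. Reword the last sentence of Section 10.5.3 to match Section 10.5: besides the Table 9 events, any SAE not covered by Section 10.5.1 or 10.5.2 is reported on the SAE form within 24 hours, in both arms, whatever the site's view of causality. Causality and expectedness are then reviewed centrally, as Section 10.6 already provides.
2. Apply the Table 8 list to participants in both arms, so that the same event follows the same route whatever the allocation. The first change alone would leave this asymmetry in place.

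The cost is a short amendment, a note to sites and a modest number of extra SAE forms. Clinical management does not change.
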